4.3.3 Treatment Details: Cycles 2+, Cohorts A & B

Larotrectinib: Oral/Nasogastric/Gastrostomy

Days: 1 - 28

Dose: 100 mg/m²/dose BID (maximum of 100 mg/dose BID).

Only use larotrectinib provided for investigational use specifically for ADVL1823.

Note that this study will enroll very young children, but the dose will be based on body surface area for all patients regardless of age.

Larotrectinib capsules should not be opened and must be swallowed whole. If vomiting occurs following dosing, doses should NOT be repeated and the next dose should be administered at the regularly scheduled time. If a dose is missed, it may be administered if there is at least 8 hours remaining until the next scheduled dose. Liquid formulation is also available and may be administered orally or via NG- or G-tube.

Drug doses should be adjusted based on the BSA calculated from height and weight measured within 7 days prior to the beginning of each cycle and according to the dosing nomogram (see [Appendix X-A](#)). Doses of larotrectinib capsules should be rounded to the nearest 25 mg ([Appendix X-A](#)). Calculated dosing volumes of larotrectinib liquid formulation should be rounded to the nearest 0.1 mL (2 mg) for doses \leq 45 mg (in oral syringes \leq 3 mL) and 0.2 mL (4 mg) for doses $>$ 45 mg (in 5-10 mL oral syringes) for the actual deliverable dose ([Appendix X-B](#)).

All patients taking larotrectinib must complete a patient diary ([Appendix VII-A](#) and [Appendix VII-B](#)).

See [Section 5.0 for Dose Modifications based on Toxicities.](#)

Patients will have disease evaluation at the end of cycles 2, 4, 6, 9, 12, 16, 20, and 24. Patients with progressive disease at any time will discontinue protocol therapy.

Patients who achieve a complete response will receive 6 additional cycles of therapy after achieving CR or a minimum of 12 cycles of therapy (whichever occurs later). Such patients will subsequently enter Follow-up ([Section 7.2](#)).

Patients who achieve sufficient tumor shrinkage to have localized, resectable disease (for whom a complete resection is anticipated to be likely without predicted functional, neurologic, or significant cosmetic deficit) will undergo surgical resection of their residual tumor after a minimum of 6 cycles of therapy. See [Section 13.1](#) for surgical guidelines. Such

patients may receive up to 1 additional cycle of therapy after their tumor is deemed resectable during surgical planning. Larotrectinib will be held for 24 hours prior to surgery. For patients who undergo resection of their tumor while on study, operative reports and hospital discharge summaries must be uploaded into RAVE following surgical resection. Following surgery, patients with IFS or CMN who achieve a gross total resection and all other patients with solid tumors who achieve a resection with negative margins ([Section 13.2](#)) will enter Follow-up ([Section 7.2](#)). Patients who have an incomplete resection or positive margins for diagnoses other than IFS/CMN ([Section 13.2](#)) will resume protocol therapy following surgery. Therapy may be resumed as soon as 24 hours post-operatively once it has been determined that the patient meets protocol criteria to resume therapy and the patient is tolerating enteral fluids.

For all other patients, following completion of this cycle, the next cycle starts on Day 29 or when the criteria in [Section 4.1.3](#) are met (whichever occurs later). Larotrectinib will be administered continuously without breaks between cycles unless the patient has progressive disease or meets criteria for holding or discontinuing larotrectinib ([Section 5.1](#)).

4.4 Cycle 1, Cohort C

4.4.1 Therapy Delivery Map – Cycle 1, Cohort C

This Therapy Delivery Map (TDM) relates to Cycle 1 for Cohort C. Each cycle lasts 28 days.

Patient COG ID number _____

DOB _____

Criteria to start each cycle are listed in [Section 4.1.3](#). Extensive treatment details are in [Section 4.4.3](#).

This TDM is 7 pages in length.

| DRUG | ROUTE | DOSAGE | DAYS | IMPORTANT NOTES |
|---|--|---|------------------------------|---|
| Methotrexate OR Cytarabine OR Triples (methotrexate/ hydrocortisone/ cytarabine) | Methotrexate Intrathecal | Age (yrs) Dose < 1 7.5 mg 1-1.99 8 mg 2-2.99 10 mg 3-8.99 12 mg ≥ 9 15 mg | -7 to -1 8, | Patients should receive one dose of intrathecal therapy between Days -7 to -1 at their physician's discretion. Day 8 for all patients. Continue weekly thereafter ONLY for patients with ALL who are CNS 2 (see Section 10.8) at enrollment until two consecutive clear CSF samples are obtained |
| | Cytarabine Intrathecal | Age (yrs) Dose < 1 20 mg 1-1.99 30 mg 2-2.99 50 mg ≥ 3 70 mg | -7 to -1 8, 15, 22 | Patients should receive one dose of intrathecal therapy between Days -7 to -1 at their physician's discretion. Days 8 and weekly thereafter only for patients with AML who have positive CSF (see Section 10.9) at enrollment until two consecutive clear CSF samples are obtained. |
| | Triples (methotrexate/ hydrocortisone/ cytarabine) Intrathecal | Age (yrs) Dose < 1 MTX: 7.5 mg, HC: 7.5 mg, ARAC: 15 mg 1-1.99 MTX: 8 mg, HC: 8 mg, ARAC: 16 mg 2-2.99 MTX: 10 mg, HC: 10 mg, ARAC: 20 mg 3-8.99 MTX: 12 mg, HC: 12 mg, ARAC: 24 mg ≥ 9 MTX: 15 mg, HC: 15 mg, ARAC: 30 mg | -7 to -1 8, 15, 22 | Patients should receive one dose of intrathecal therapy between Days -7 to -1 at their physician's discretion. Days 8, 15, and 22 only for patients with ALL who are CNS 3 (see Section 10.8) at enrollment and regardless of whether or not the patient clears. Patients who do not clear by the end of cycle 1 will be removed from protocol therapy. |

| | | | | |
|------------------------------|--|---------------------------------|--------|---|
| Larotrectinib IND# 141824 | Oral/Nasogastric/ Gastrostomy Tube | 100 mg/m ² /dose BID | 1 – 28 | Maximum dose = 100 mg/dose BID. See Appendix X-A and Appendix X-B for dosing nomograms. |
|------------------------------|--|---------------------------------|--------|---|

| Ht _____ cm | | | Wt _____ kg | | | BSA _____ m ² | |
|--|------------|----------|---|--------------------------|------------------------|----------------------------|----------------|
| Date Due | Date Given | Day | Larotrectinib AM dose: _____ mg PM dose: _____ mg | Methotrexate _____ mg | Cytarabine _____ mg | Hydrocortisone _____ mg | Studies |
| Enter calculated dose above and actual dose administered below | | | | | | | |
| | Pre- | AM Dose | PM Dose | _____ mg | _____ mg | _____ mg | a – j, l, m, o |
| | 1 | _____ mg | _____ mg | | | | |
| | 2 | _____ mg | _____ mg | | | | |
| | 3 | _____ mg | _____ mg | | | | |
| | 4 | _____ mg | _____ mg | | | | |
| | 5 | _____ mg | _____ mg | | | | |
| | 6 | _____ mg | _____ mg | | | | |
| | 7 | _____ mg | _____ mg | | | | |
| | 8 | _____ mg | _____ mg | _____ mg | _____ mg | _____ mg | j, k |
| | 9 | _____ mg | _____ mg | | | | |
| | 10 | _____ mg | _____ mg | | | | |
| | 11 | _____ mg | _____ mg | | | | |
| | 12 | _____ mg | _____ mg | | | | |
| | 13 | _____ mg | _____ mg | | | | |
| | 14 | _____ mg | _____ mg | | | | |
| | 15 | _____ mg | _____ mg | _____ mg | _____ mg | _____ mg | j – l |
| | 16 | _____ mg | _____ mg | | | | |
| | 17 | _____ mg | _____ mg | | | | |
| | 18 | _____ mg | _____ mg | | | | |
| | 19 | _____ mg | _____ mg | | | | |
| | 20 | _____ mg | _____ mg | | | | |
| | 21 | _____ mg | _____ mg | | | | |

| | | | | | | | | | |
|--|--|----|----------|----------|----------|----------|----------|------------|---|
| | | 22 | _____ mg | j, k | d |
| | | 23 | _____ mg | _____ mg | | | | | |
| | | 24 | _____ mg | _____ mg | | | | | |
| | | 25 | _____ mg | _____ mg | | | | | |
| | | 26 | _____ mg | _____ mg | | | | | |
| | | 27 | _____ mg | _____ mg | | | | | |
| | | 28 | _____ mg | _____ mg | | | | h, j, k, n | |

See [Section 5.0](#) for Dose Modifications for Toxicities and the COG Member website for Supportive Care Guidelines.

4.4.2 Required Observations in Cycle 1, Cohort C

All baseline studies must be performed prior to starting protocol therapy unless otherwise indicated below.

- a. Hx/Wt /Ht/BSA. Within 7 days prior to Cycle 1.
- b. Performance status. Prior to Cycle 1.
- c. Physical exam (including VS and neurologic examination). Prior to Cycle 1.
- d. CBC/diff/platelets: Prior to Cycle 1 and every week during Cycle 1. If patients have Grade 4 neutropenia then CBCs should be checked every 3 to 4 days until recovery to Grade 3 or until meeting the criteria for dose limiting toxicity.
- e. Electrolytes including Ca⁺⁺. Prior to Cycle 1.
- f. Creatinine, ALT, bilirubin. Prior to Cycle 1.
- g. Albumin. Prior to Cycle 1.
- h. Bone marrow evaluation, lumbar puncture, and evaluation of any sites of extramedullary disease. Prior to Cycle 1 and at the end of Cycle 1.
- i. Pregnancy test. Prior to Cycle 1. Female patients of childbearing potential require a negative pregnancy test prior to starting treatment; sexually active patients must use an acceptable method of birth control.
- j. Cerebral spinal fluid (CSF) cell count and differential. Within 7 days prior to Cycle 1 and at the end of Cycle 1. CSF will be obtained on Days 8, 15, and 22 only for patients who are receiving intrathecal therapy on that date.
- k. Cerebral spinal fluid (CSF) and peripheral blood pharmacokinetics. At the end of Cycle 1 at the time of the first disease evaluation for all patients with leukemia, and on Days 8, 15, and 22 for patients who are receiving intrathecal therapy. See [Section 7.3.3](#) for details.

1. Circulating tumor DNA. Prior to Cycle 1 and on Day 15 of Cycle 1. See [Section 7.3.2](#) for details.
- m. Tumor tissue submission. Prior to Cycle 1. If tissue blocks or slides are unavailable, the study chair must be notified prior to study enrollment. See [Section 7.3.1](#) for details.
- n. Patient diary. Uploaded into RAVE at the end of Cycle 1. See [Appendix VII-A](#) and [Appendix VII-B](#) for details.
- o. Neurocognitive assessments. Within 4 weeks after enrollment. See [Section 3.1.7](#) and [Appendix XI](#) for details.

This listing only includes evaluations necessary to answer the primary and secondary aims. OBTAIN OTHER STUDIES AS REQUIRED FOR GOOD CLINICAL CARE.

Comments

(Include any held doses, or dose modifications)

4.4.3 Treatment Details: Cycle 1, Cohort C

Baseline Methotrexate, Cytarabine, OR Triples (Methotrexate/Hydrocortisone/Cytarabine): Intrathecal
Day: -7 to -1

Dose: A single dose of intrathecal methotrexate or triples should be administered at the treating physician's discretion within 7 days of Day 1 of Cycle 1 of therapy for patients in Cohort C with ALL. A single dose of intrathecal cytarabine should be administered at the treating physician's discretion within 7 days of Day 1 of Cycle 1 of therapy for patients in Cohort C with AML.

See age-based dosing recommendations below. Note: Intrathecal therapy received prior to enrollment within 7 days prior to Day 1 of Cycle 1 will replace the pre-Cycle 1 intrathecal, even if administered at different doses.

Methotrexate: Intrathecal

Days: 8 for all patients. Continue weekly thereafter ONLY for patients with ALL who are CNS 2 (see [Section 10.8](#)) at enrollment until two consecutive clear CSF samples are obtained.

| Age (yrs) | Dose |
|------------------|-------------|
| <1 | 7.5 mg |
| 1-1.99 | 8 mg |
| 2-2.99 | 10 mg |
| 3-8.99 | 12 mg |
| ≥ 9 | 15 mg |

Cytarabine: Intrathecal

Days: 8 and weekly thereafter ONLY for patients with AML who have positive CSF (see [Section 10.9](#)) at enrollment until two consecutive clear CSF samples are obtained.

| Age (yrs) | Dose |
|------------------|-------------|
| < 1 | 20 mg |
| 1-1.99 | 30 mg |
| 2-2.99 | 50 mg |
| ≥ 3 | 70 mg |

Methotrexate (MTX)/Hydrocortisone (HC)/Cytarabine (ARAC): Intrathecal

Days: 1, 8, 15, and 22 ONLY for patients with ALL who are CNS 3 (see [Section 10.8](#)) at enrollment. Thereafter, weekly intrathecals should continue until 2 clear CSF samples are obtained, and regardless of whether or not the

patient clears. Thereafter, weekly intrathecals should continue until 2 clear CSF samples are obtained. Patients who do not clear by the end of cycle 1 will be removed from protocol therapy.

| Age (yrs) | Dose |
|------------------|--------------------------------------|
| <1 | MTX: 7.5 mg, HC: 7.5 mg, ARAC: 15 mg |
| 1-1.99 | MTX: 8 mg, HC: 8 mg, ARAC: 16 mg |
| 2-2.99 | MTX: 10 mg, HC: 10 mg, ARAC: 20 mg |
| 3-8.99 | MTX: 12 mg, HC: 12 mg, ARAC: 24 mg |
| ≥ 9 | MTX: 15 mg, HC: 15 mg, ARAC: 30 mg |

Larotrectinib: Oral/Nasogastric/Gastrostomy

Days: 1 - 28

Dose: 100 mg/m²/dose BID (maximum of 100 mg/dose BID).

Only use larotrectinib provided for investigational use specifically for ADVL1823.

Note that this study will enroll very young children, but the dose will be based on body surface area for all patients regardless of age.

Larotrectinib capsules should not be opened and must be swallowed whole. If vomiting occurs following dosing, doses should NOT be repeated and the next dose should be administered at the regularly scheduled time. If a dose is missed, it may be administered if there is at least 8 hours remaining until the next scheduled dose. Liquid formulation is also available and may be administered orally or via NG- or G- tube.

Drug doses should be adjusted based on the BSA calculated from height and weight measured within 7 days prior to the beginning of each cycle and according to the dosing nomogram (see [Appendix X-A](#)). Doses of larotrectinib capsules should be rounded to the nearest 25 mg ([Appendix X-A](#)). Calculated dosing volumes of larotrectinib liquid formulation should be rounded to the nearest 0.1 mL (2 mg) for doses ≤ 45 mg (in oral syringes ≤ 3 mL) and 0.2 mL (4 mg) for doses > 45 mg (in 5-10 mL oral syringes) for the actual deliverable dose ([Appendix X-B](#)).

All patients taking larotrectinib must complete a patient diary ([Appendix VII-A](#) and [Appendix VII-B](#)).

See [Section 5.0 for Dose Modifications based on Toxicities.](#)

Following completion of Cycle 1, patients with leukemia will have a disease evaluation. Patients with progressive disease or treatment failure will discontinue protocol therapy.

For all other patients, the next cycle ([Section 4.6](#)) starts on Day 29 or when the criteria in [Section 4.1.3](#) are met (whichever occurs later). Patients achieving a response may discontinue protocol therapy at their physician's discretion to receive consolidative therapy (e.g. transplant).

Larotrectinib will be administered continuously without breaks between cycles unless the patient meets criteria for holding or discontinuing larotrectinib ([Section 5.1](#)).

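### Cohort C's intrathecal instructions are internally inconsistent on Day 1 triples, on who receives Day 8 methotrexate, and on weekly dosing after Day 22

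*Combined protocol and SAP*

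**What the plan says.** **Baseline dose.** Section 4.4.1 states: "Patients should receive one dose of intrathecal therapy between Days -7 to -1 at their physician's discretion". Section 4.4.3 opens with the same window and names the drugs: methotrexate or triples for ALL, cytarabine for AML.

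**Triples, CNS 3 ALL.** Section 4.4.3 gives "Days: 1, 8, 15, and 22 ONLY for patients with ALL who are CNS 3". Section 4.4.1 gives "Days 8, 15, and 22 only for patients with ALL who are CNS 3". The day-by-day grid in Section 4.4.1 has intrathecal fields in the pre-cycle row and on Days 8, 15 and 22. Its Day 1 row has larotrectinib fields only.

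**Methotrexate, Day 8.** Section 4.4.3: "Days: 8 for all patients. Continue weekly thereafter ONLY for patients with ALL who are CNS 2". Section 4.4.1: "Day 8 for all patients. Continue weekly thereafter ONLY for patients with ALL who are CNS 2". Neither limits the Day 8 dose by leukemia type or CNS status.

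**Cytarabine, Day 8.** Section 4.4.3: "Days: 8 and weekly thereafter ONLY for patients with AML who have positive CSF". The map's row has the same restriction.

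**How the rows relate.** The map's drug cell reads "Methotrexate OR Cytarabine OR Triples". In Section 4.4.3 only the baseline block is headed as a choice of drugs. The Day 8 blocks stand separately.

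**After Day 22, CNS 3 ALL.** Section 4.4.3 continues weekly dosing until two clear CSF samples, adds that this holds whether or not the patient clears, and then repeats the continuation sentence. In the map, the clause about clearing attaches only to Days 8, 15 and 22. Both sections carry the removal rule: "Patients who do not clear by the end of cycle 1 will be removed from protocol therapy". Sections 4.5.1 and 4.5.3 give one intrathecal dose per cycle from Cycle 2, in the window Day -3 to Day 1, and restrict single-agent methotrexate to ALL.

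**The concern.** These are operative rules for intrathecal chemotherapy, and a site can comply with one part of the protocol while departing from another. Three questions have no single answer in the text:

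- Does a CNS 3 ALL patient have a Day 1 intrathecal dose?
- Does an AML patient receive methotrexate on Day 8?
- What applies from Cycle 2 to a CNS 3 patient who has cleared but does not yet have two clear samples?

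What is at stake is consistent treatment within Cohort C and the ability to say what counts as a protocol deviation. For the second question, it is also which patients contribute a Day 8 CSF and plasma pair to exploratory Aim 1.3.10.

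**Working it through.** No sample size, power or error rate depends on this point. The check is a side-by-side reading with a count of doses.

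**1. Day 1 triples in CNS 3 ALL.** Cycle 1 intrathecal administrations, baseline included and the separate methotrexate row left aside:

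- Map and grid (Section 4.4.1): 1 baseline + 3 (Days 8, 15, 22) = 4.
- Treatment details (Section 4.4.3): 1 baseline + 4 (Days 1, 8, 15, 22) = 5.

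The difference is the Day 1 entry. It does not replace the baseline dose, because Section 4.4.3 has its own baseline block. If the baseline dose fell on Day -1, the two doses would be only 1 to 2 days apart.

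**2. Day 8 methotrexate.** The two sections agree with each other here. The unrestricted wording conflicts with the text around it:

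| Group | Day 8 by the group's own row | If the unrestricted wording is added |
|---|---|---|
| AML, CSF negative | nothing | methotrexate |
| AML, CSF positive | cytarabine | cytarabine and methotrexate |
| ALL, CNS 3 | triples (contain methotrexate) | triples and methotrexate |

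For CSF-negative AML the Cycle 1 count is 1 by the cytarabine row, or 1 + 1 = 2 if Day 8 methotrexate applies. Three other places sit badly with an unrestricted rule:

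- The map presents the regimens as alternatives.
- Single-agent methotrexate in Cycles 2+ is for ALL only (Sections 4.5.1 and 4.5.3).
- Day 8 CSF and pharmacokinetic sampling is conditional on receiving intrathecal therapy (Sections 4.4.2 and 7.3.3.2). That condition would have no effect on Day 8 if everyone were treated.

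The sampling consequence for CSF-negative AML is 1 CSF and plasma pair in Cycle 1 (end of cycle), or 2 if Day 8 counts.

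**3. Weekly dosing after Day 22 in CNS 3 ALL.** Cycles last 28 days.

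- Next weekly dose: Day 22 + 7 = 29, and 29 - 28 = Cycle 2 Day 1. This lies inside the Cycle 2 window, so there is no conflict.
- The dose after that: Day 29 + 7 = 36, and 36 - 28 = Cycle 2 Day 8. This has no place in a schedule of one dose per cycle.

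Take a patient whose first clear CSF is at the end-of-Cycle-1 lumbar puncture. The documents do not say whether one clear sample is enough to count as cleared under the removal rule.

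- If one is enough, the patient stays on therapy. Section 4.4.3 then calls for weekly doses until a second clear sample, while Section 4.5.3 calls for a single dose per cycle.
- If two are needed, the patient is removed and the weekly rule never applies.

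The clause continuing therapy whether or not the patient clears gives the weekly rule no end point if read literally.

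**The case against.** **Duplicate methotrexate.** A reader might infer that CNS 3 ALL patients are scheduled for two methotrexate-containing treatments on Day 8, for example 15 mg + 15 mg at age 9 or over. That follows only if the rows are read as additive. The map's heading makes them alternatives, and its grid has one methotrexate column with a single Day 8 field. Duplicate dosing is therefore unlikely for a site working from the map. What stands is that the Day 8 blocks in Section 4.4.3 carry no such limit, and the heading does not tell a site whether CSF-negative AML gets methotrexate or nothing on Day 8.

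**Disagreement between sections on Day 8.** A reader might also infer that Sections 4.4.1 and 4.4.3 contradict each other on this dose. They do not; their wording matches. The map's methotrexate days cell ends in a stray comma, so some text may have been lost in extraction. The notes column and Section 4.4.3 are nevertheless complete and unrestricted.

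**Removal rule.** Fixed doses through Day 22 followed by removal of patients who have not cleared is a coherent sequence. The repeated sentence in Section 4.4.3 looks like an editing remnant. Both points are fair. The conflict is narrower: one instance of the weekly continuation already has no counterpart in the map or in the Cycles 2+ schedule.

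**Practical reach.** Section 2.7.1 reports accrual complete, and Section 3.1.5 requires therapy to be projected to start within five days of enrollment. The documents therefore point to no future Cycle 1 patient. This lowers the urgency, but any Cohort C treatment already given still has to be judged against one schedule.

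**Conclusion.** The inconsistency is real and is a drafting defect. For CNS 3 ALL the literal Cycle 1 count is 5 in Section 4.4.3 and 4 in Section 4.4.1. Day 8 methotrexate is ambiguous mainly for AML, where a CSF-negative patient has 1 or 2 Cycle 1 doses depending on the reading. The weekly continuation creates competing rules only for a CNS 3 patient who counts as cleared without two clear samples. That case assumes one clear sample satisfies the removal rule, which the protocol leaves undefined.

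The documents do not support a wider reading. Cohort C is exploratory and reported descriptively, so the two-stage design and inference in Cohort A are unaffected. Pharmacokinetic sampling in Cycle 1 is on Days 8, 15 and 22 and at the end of the cycle. Neither the Day 1 discrepancy nor dosing after Day 22 changes it; only the Day 8 wording can. The documents do not give the number of Cohort C patients, and if none enrolled the effect on data is nil. The text deserves correction, but it does not threaten the trial's main conclusions.

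**What to change.** The sponsor should reconcile Sections 4.4.1 (map and grid), 4.4.2, 4.4.3, 4.5.1 and 4.5.3 into one intrathecal schedule, set out by leukemia type and CNS status. It should state:

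- whether there is a Day 1 dose in addition to baseline;
- which patients the Day 8 methotrexate instruction covers, with the conditional Day 8 CSF and pharmacokinetic sampling aligned to the answer;
- how many clear samples count as cleared at the end of Cycle 1, and how any weekly continuation fits with removal and with one dose per cycle afterwards.

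The repeated sentence in Section 4.4.3 should be removed. The clinical team must decide the content, and no schedule is preferred here. If Cohort C patients were treated, the report should state which schedule was used to judge deviations and to define the expected Day 8 samples. The cost is protocol wording only.

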4.5 Therapy Subsequent to Cycle 1 (Cycles 2+), Cohort C

4.5.1 Therapy Delivery Map – Cycles 2+, Cohort C

This Therapy Delivery Map (TDM) relates to Cycles 2+ for Cohort C. Each cycle lasts 28 days.

Patient COG ID number

DOB

Criteria to start each cycle are listed in [Section 4.1.3](#). Extensive treatment details are in [Section 4.5.3](#).

This TDM is on 7 pages.

| DRUG | ROUTE | DOSAGE | | DAYS | IMPORTANT NOTES |
|---|---|---------------------------------|---|---------|---|
| Methotrexate OR Cytarabine OR Triples (methotrexate/ hydrocortisone/ cytarabine) | Methotrexate | Intrathecal | Age (yrs) Dose < 1 7.5 mg 1-1.99 8 mg 2-2.99 10 mg 3-8.99 12 mg ≥ 9 15 mg | -3 to 1 | Patients with ALL ONLY. Patients should receive one dose of intrathecal therapy between Days -3 to 1 of each cycle. |
| | Cytarabine | Intrathecal | Age (yrs) Dose < 1 20 mg 1-1.99 30 mg 2-2.99 50 mg ≥ 3 70 mg | -3 to 1 | Patients with AML ONLY. Patients should receive one dose of intrathecal therapy between Days -3 to 1 of each cycle. |
| | Triples (methotrexate/ hydrocortisone/ cytarabine) | Intrathecal | Age (yrs) Dose < 1 MTX: 7.5 mg, HC: 7.5 mg, ARAC: 15 mg 1-1.99 MTX: 8 mg, HC: 8 mg, ARAC: 16 mg 2-2.99 MTX: 10 mg, HC: 10 mg, ARAC: 20 mg 3-8.99 MTX: 12 mg, HC: 12 mg, ARAC: 24 mg ≥ 9 MTX: 15 mg, HC: 15 mg, ARAC: 30 mg | -3 to 1 | Patients with ALL who are CNS 3 (see Section 10.8) at enrollment may receive either methotrexate or triples at their physician's discretion. Patients should receive one dose of intrathecal therapy between Days -3 to 1 of each cycle. |
| Larotrectinib IND# 141824 | Oral/Nasogastric/ Gastrostomy Tube | 100 mg/m ² /dose BID | | 1 – 28 | Maximum dose = 100 mg/dose BID. See Appendix X-A and Appendix X-B for dosing nomograms. |

Ht _____ cm

Wt _____ kg

BSA _____ m²

CYCLE # _____

| Date Due | Date Given | Day | Larotrectinib AM dose: _____ mg PM dose: _____ mg | Methotrexate _____ mg | Cytarabine _____ mg | Hydrocortisone _____ mg | Studies |
|--|------------|------|---|--------------------------|------------------------|----------------------------|--------------|
| Enter calculated dose above and actual dose administered below | | | | | | | |
| | | Pre- | AM Dose | PM Dose | | | a – j, l – n |
| | | 1 | _____ mg | _____ mg | _____ mg | _____ mg | i |
| | | 2 | _____ mg | _____ mg | | | |
| | | 3 | _____ mg | _____ mg | | | |
| | | 4 | _____ mg | _____ mg | | | |
| | | 5 | _____ mg | _____ mg | | | |
| | | 6 | _____ mg | _____ mg | | | |
| | | 7 | _____ mg | _____ mg | | | |
| | | 8 | _____ mg | _____ mg | | | |
| | | 9 | _____ mg | _____ mg | | | |
| | | 10 | _____ mg | _____ mg | | | |
| | | 11 | _____ mg | _____ mg | | | |
| | | 12 | _____ mg | _____ mg | | | |
| | | 13 | _____ mg | _____ mg | | | |
| | | 14 | _____ mg | _____ mg | | | |
| | | 15 | _____ mg | _____ mg | | | |
| | | 16 | _____ mg | _____ mg | | | |
| | | 17 | _____ mg | _____ mg | | | |
| | | 18 | _____ mg | _____ mg | | | |
| | | 19 | _____ mg | _____ mg | | | |
| | | 20 | _____ mg | _____ mg | | | |
| | | 21 | _____ mg | _____ mg | | | |
| | | 22 | _____ mg | _____ mg | | | |

| | | | | | | | | |
|--|--|----|----------|----------|--|--|--|---|
| | | 23 | _____ mg | _____ mg | | | | |
| | | 24 | _____ mg | _____ mg | | | | |
| | | 25 | _____ mg | _____ mg | | | | |
| | | 26 | _____ mg | _____ mg | | | | |
| | | 27 | _____ mg | _____ mg | | | | |
| | | 28 | _____ mg | _____ mg | | | | k |

See [Section 5.0](#) for Dose Modifications for Toxicities and the COG Member website for Supportive Care Guidelines.

